19.6. Safety Analysis

All subjects who receive at least 1 dose of study drug will be included in the safety analyses. Safety data will be summarized descriptively or graphically, as appropriate.

19.6.1. Adverse Events

Adverse events will be coded using the appropriate version of MedDRA. All AEs will be presented in a data listing. Only treatment-emergent adverse events (TEAEs) (events that are new in onset or aggravated in severity following treatment) will be included in all summaries. TEAEs will be summarized for each treatment group, by system organ class and preferred term. Serious adverse events (including death) will be summarized. In addition, adverse events will be summarized by severity and relation to study drug.

19.6.2. Clinical Laboratory Tests

Hematology, blood chemistry, and urinalysis results will be summarized at baseline and at each visit by treatment group. Change from baseline to each visit will also be summarized. Abnormal laboratory values will be identified and analyzed.

19.6.3. Vital Signs

Vital sign results (heart rate, diastolic/systolic blood pressures, respiratory rate, and body temperature) and corresponding changes from baseline values will be summarized at each visit with descriptive statistics by treatment group.

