7.2. Schedule of Study Events

Table 1: Schedule of Study Events

Assessment/Procedure	Screening (Day -42 to Day -1)	Baseline ^a	Treatment Period		Follow-up Visit 1	End of Study/ Follow-up Visit 2/
		Day 1	Day 7 (± 1 day)	Day 14 (± 2 days) ^b	Day 21 (± 2 days)	Day 42 (± 2 days)
Informed Consent	X					
Inclusion/Exclusion Criteria Review	X	X				
Medical/Surgical History	X					
Current Medical Condition Review		X	X		X	X
Demographics	X					
Complete Physical Examination		X				X
Limited Physical Examination	X		X		X	
Height and Weight ^c	X	X				X
Vital Signs ^d	X	X	X		X	X
12-lead ECG		X				X
Clinical Laboratory Tests ^e	X	X	X		X	X
HbA1c	X					
Serum Pregnancy Test	X					X
Urine Pregnancy Test		X	X		X	
Hepatitis Serology	X					
IGRA for TB	X					
EDSS/FSS	X	X	X		X	X

Assessment/Procedure	Screening (Day -42 to Day -1)	Baseline ^a	Treatment Period		Follow-up Visit 1	End of Study/ Follow-up Visit 2/
		Day 1	Day 7 (± 1 day)	Day 14 (± 2 days) ^b	Day 21 (± 2 days)	Day 42 (± 2 days)
MSIS-29	X	X	X	X	X	X
CGI-I			X		X	X
████		X			X	X
██████████		X			X	X
████		X			X	X
Study Drug and Diary Training		X				
IXRS Contact	X	X				
Dispense Study Drug		X				
Administer First Dose ^f		X				
Study Drug Accountability and Diary Review			X		X	
Adverse Events and Concomitant Treatments	X					

^a The Baseline visit will occur 14 (± 1) days after the first dose of IVMP, oral prednisone or oral methylprednisolone.

^b All Day 14 assessments will be done via telephone.

^c Height will be collected at the Screening Visit only.

^d Blood pressure, pulse rate, respiratory rate and body temperature. Blood pressure will be measured in triplicate at the Screening and Baseline Visits.

^e Chemistry, hematology, and urinalysis.

^f The first dose will be administered clinic and the subject will be observed for at least 1 hour after dosing.

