9.5. Adverse Events

The most common adverse reactions for Acthar [REDACTED] include fluid retention, alteration in glucose tolerance, elevation of blood pressure, behavioral and mood changes, and increased appetite and weight gain. See the current Acthar package insert for more specific information on adverse events associated with Acthar ([Mallinckrodt, \[REDACTED\]](#)).

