10. Subjects must have a mean systolic blood pressure ≤ 140 mm Hg and a mean diastolic blood pressure of ≤ 90 mm Hg determined by the average of 3 seated readings taken at least 5 minutes apart at the Screening and Baseline Visits.
11. Subjects must be able to communicate effectively with study personnel.
12. Subjects must be able and willing to follow all protocol requirements and study restrictions.

13. Subjects must be able and willing to return for all study visits.

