15.3.1. Treatment Discontinuation

Treatment with study drug should be discontinued if any of the following occur:

- Development of accelerated hypertension (defined as systolic blood pressure \geq 180 *and* diastolic blood pressure \geq 100 mm Hg) that cannot be managed by the adjustment of concomitant medications such as antihypertensive medications.
- Development of congestive heart failure that cannot be managed by the adjustment of concomitant medications such as diuretics and antihypertensive medications.
- Development of diabetic signs/symptoms (ie, HbA1c $>$ 6.5%, or fasting plasma glucose $>$ 126 mg/dL, or classic symptoms of hyperglycemia with random plasma glucose $>$ 200 mg/dL).
- Subjects who undergo plasma exchange or IVIg due to lack of efficacy will be considered treatment failures and will be withdrawn from the study.
- Development of any other AE of at least moderate intensity and possibly, probably or definitely related to study drug that cannot be managed by the adjustment of concomitant medications.

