17.6. Vital Signs

Vital signs will be obtained after the subject has been seated for 5 minutes (minimum) and will include systolic and diastolic blood pressures, pulse rate, respiratory rate, and body temperature. Additionally, at the Screening and Baseline Visits, blood pressure will be measured at least 3 times, with 5 minutes between assessments after the subject has been seated for a minimum of 5 minutes prior to the initial blood pressure assessment. The date and time for all vital sign assessments will be recorded.

The investigator may perform additional unscheduled vital sign measurements to evaluate or manage a suspected AE. These unscheduled vital sign measurements should be obtained after the subject has been seated for at least 5 minutes, if possible. Unscheduled vital signs will be recorded.

Screening/Baseline Assessments

A subject with systolic blood pressure > 140 mm Hg and diastolic blood pressure > 90 mm Hg (average of 3 assessments) at the Screening or Baseline Visits does not qualify for the study.

On Study Assessments

If an on study vital sign is not in the site's standard reference range, an AE will be recorded if the investigator determines the change is clinically significant or requires a change in the subject's clinical management.

17.7. Clinical Laboratory Tests (Chemistry, Hematology, Urinalysis, HbA1c, Hepatitis Serology, IGRA, and Pregnancy Tests)

The clinical laboratory tests are listed in [Section 31.1](#). All clinical laboratory tests will be done at a central laboratory facility except urine pregnancy (at the site) and IGRA (local laboratory). Specific instructions for collection, processing, storage, and shipment of clinical laboratory samples will be provided in a separate laboratory manual, where appropriate.

Samples for laboratory testing at all visits may be collected under fasted or nonfasted conditions. Fasting early morning samples are preferred, but a random daytime sample is acceptable. The date and time of the sample collection must be documented on the laboratory report. Investigators must review and sign laboratory reports. The clinical significance of each laboratory abnormality will be documented. New clinically significant laboratory abnormalities or clinically significant changes in laboratory values will be reported as AEs, as appropriate.

Hematology with differential, serum chemistry, and urinalysis samples will be collected at the specific times starting at screening and throughout the study.

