21. SUBJECT DISCONTINUATION OR WITHDRAWAL

21.1. Subject Withdrawal

Subjects who discontinue, or are withdrawn from the study for any reason, will be required to enter the follow-up period and have the Early Termination and Follow-up safety assessments (see [Section 14.5](#) and [Section 14.6](#)) to assess their continued well-being.

The reason for discontinuation will be recorded. A subject may be discontinued from the study for the following medical or administrative reasons:

Withdrawal by Subject

Subjects will be free to discontinue from the study at any time. Subjects who have received at least 1 dose of study drug but do not complete the study will not be replaced.

Lack of Efficacy

Subjects who undergo plasma exchange or receive IVIg following treatment with Acthar due to lack of efficacy will be considered treatment failures and will be withdrawn from the study.

Adverse Event

If a dosed subject suffers an AE that, in the judgment of the investigator, sponsor or MM, presents an unacceptable consequence or risk to the subject, the subject will be discontinued from further participation in the study.

Death

In the event that a subject dies during the study, death will be the reason for discontinuation.

Lost to Follow-up

Every effort should be used to maintain contact with subjects during their participation in the study. A subject may be considered lost to follow up if there is no response to 3 attempts to reach the subject by telephone and no response to a certified letter sent to the last known address of the subject. Efforts to contact the subject should be noted in source documentation.

Met Withdrawal Criteria

If a subject develops a condition that meets any of the exclusion criteria ([Section 12.2](#)) or fails to meet an inclusion criteria ([Section 12.1](#)) during the study that is not considered to be an AE or is noncompliant (eg, has a positive pregnancy during the screening or treatment periods or positive drug screening test), the subject will be discontinued from further participation in the study. Discontinuation is also mandated for safety and/or tolerability issues as outlined in [Section 15.3.1](#).

Other

If the above reasons are not applicable, please use the “Other” option and provide the appropriate reason for subject withdrawal.

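### Blood pressure is summarised only visit by visit, so how many subjects had a rise is counted only through investigator-reported AEs; a per-subject table would close the gap cheaply

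*Combined protocol and SAP*

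**What the plan says.** **The harm.** Section 9.5 lists "fluid retention, alteration in glucose tolerance, elevation of blood pressure, behavioral and mood changes" among the most common reactions to Acthar. Safety and tolerability is a primary objective (Section 10.1). Section 19.3.2 defines the primary safety endpoint to include vital signs, both per study period and across the whole study.

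**The analysis.** For vital signs Section 19.6.3 plans that values and "corresponding changes from baseline values will be summarized at each visit with descriptive statistics by treatment group". Section 19.1 defines descriptive statistics for numerical variables as n, mean, SD, median, minimum and maximum. For laboratory data, Section 19.6.2 adds a sentence committing to identify and analyse abnormal values. Section 19.6.3 has no counterpart.

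**The readings.** Table 1 in Section 7.2 schedules vital signs at Screening, Baseline and Days 7, 21 and 42. On Day 14 there are none: "All Day 14 assessments will be done via telephone". Section 17.6 allows extra readings ("The investigator may perform additional unscheduled vital sign measurements to evaluate or manage a suspected AE") and requires them to be recorded.

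**The AE route.** Under Section 17.6, an on-study vital sign outside the site's reference range becomes an AE if the investigator finds it clinically significant or if it calls for a change in management. Section 19.6.1 tabulates treatment-emergent AEs by arm, system organ class and preferred term, and also by severity and relatedness. Section 20.5 makes elevated blood pressure an event of special interest when systolic is at least 180 and diastolic at least 100 mm Hg. Section 19.6.1 plans no table of such events.

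**Withdrawals.** Section 15.3.1 lists accelerated hypertension "that cannot be managed by the adjustment of concomitant medications such as antihypertensive medications" as a reason to stop study drug. Section 21.1 requires anyone withdrawn to have the Early Termination and Follow-up safety assessments, and Sections 14.5 and 14.6 both include vital signs.

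**The concern.** The safety question for a drug with a known pressor effect is how many subjects had a meaningful rise. A by-visit summary answers a different question: where the distribution sat on three days. A subject who rises between visits, or whose pressure has settled by the next visit, leaves little trace in it. The maximum at a visit shows one extreme scheduled value, not how many subjects rose.

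A per-subject count then comes only from the AE tables, which depend on investigator judgement. An untreated rise judged not clinically significant is not counted anywhere. The whole-study part of the Section 19.3.2 endpoint has no matching blood pressure analysis in Section 19.6.3. In a pilot meant to inform a larger trial, the safety report could show little visit-level change although several subjects had a rise.

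**Working it through.** The documents state no figure for this point, so there is none to reproduce. The check is of text and timing, followed by an illustration.

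**1. When readings fall relative to dosing.** Inputs: 14 daily doses from Day 1 (Section 15.3) and the visit windows in Table 1.
- Day 7 (±1) is Day 6 to Day 8, within the course.
- Day 21 (±2) is Day 19 to Day 23. Against a Day 14 last dose: 19 − 14 = 5 and 23 − 14 = 9, so 5 to 9 days after.
- Day 42 (±2) is Day 40 to Day 44: 40 − 14 = 26 and 44 − 14 = 30, so 26 to 30 days after.

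One of the three post-baseline visits is on treatment. A rise confined to the second week is visible only through an unscheduled reading or an AE report.

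**2. Which planned output would count a subject with a rise?**

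| Type of rise | By-visit summary (19.6.3) | AE tables (19.6.1) |
|---|---|---|
| Present at a scheduled visit, judged not significant, untreated | Contributes to the mean; may set the maximum; not counted | No |
| Between visits, unscheduled reading, judged not significant, untreated | No rule to include it | No |
| Out of range and clinically significant, or management changed | Only if present at a visit; a later reading may be lowered by treatment | Yes |
| Meets the Section 20.5 limits | As above | As an AE, but with no special-interest table |

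The gap is the first two rows, plus the missing table in the fourth.

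**3. How far could a few rises move a by-visit mean?** Assumptions, not from the documents: k subjects in an arm rise by R mm Hg, all caught at one scheduled visit; SD of change 10 to 15 mm Hg; 33 per arm (the number randomised in Section 19.9, supposing all are dosed).

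Shift in arm mean = k × R / 33.
- k = 1, R = 20: 20/33 = 0.6
- k = 3, R = 40: 120/33 = 3.6, or 1.8 if the captured rise averages half
- k = 5, R = 40: 200/33 = 6.1
- None caught at the visit: 0

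90% half-width for the difference between arms = 1.645 × SD × √(2/33).
- SD 10: 4.1
- SD 12: 4.9
- SD 15: 6.1

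Over most of this range the shift is smaller than the half-width.

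**4. What a count would show.** With the 90% Wilson interval the plan already uses for response rates, and 33 subjects:
- 1/33 = 3.0% (0.7% to 12.5%)
- 3/33 = 9.1% (3.7% to 20.7%)
- 5/33 = 15.2% (7.6% to 28.0%)

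The intervals are wide, but they describe the number of subjects affected, which the by-visit summary does not.

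**5. Entry limits as a reference.** Inclusion criterion 10 in Section 12.1 reads "Subjects must have a mean systolic blood pressure ≤ 140 mm Hg and a mean diastolic blood pressure of ≤ 90 mm Hg", averaged over three readings. The screening rule in Section 17.6 disqualifies a subject with systolic above 140 and diastolic above 90. Read literally, a subject above one limit only fails criterion 10 but is not excluded by Section 17.6. These must be reconciled. Until they are, a count of subjects exceeding the limits after dosing should be restricted to those within both at baseline.

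**The case against.** The case against is substantial, and much of it stands.

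- **A reader might infer that blood pressure is seen only through means.** It is not. The summaries include minimum and maximum, and rises also reach the AE tables by arm. Section 19.4.3 tabulates concomitant medications by arm, and Section 19.4.4 summarises reasons for discontinuation.
- **A reader might infer that treated rises are left out.** The documents do not support that. Starting or adjusting an antihypertensive is a change in management, so under Section 17.6 an out-of-range reading that prompts it is an AE. The later reading stays in the summary, possibly lowered by treatment.
- **A reader might infer that withdrawn subjects are left out.** They are not. Section 21.1 says "Discontinuation is also mandated for safety and/or tolerability issues as outlined in" Section 15.3.1, but it also requires follow-up assessments with vital signs, and Section 19.6 keeps every dosed subject in the safety analyses. What remains is that the plan does not say to which visit an early-termination reading belongs, and later visits can be missing.
- **One on-treatment visit is a limit of the schedule.** True. New tables add no reading; they only use unscheduled readings that were taken.
- **A count of single readings is noisy.** True. Entry uses an average of three, so subjects near a limit will cross it by chance in both arms.
- **Detail is deferred.** Section 19.1 calls Section 19 a general description and promises a separate, more detailed SAP, which is not among the documents reviewed. Silence here is not a stated exclusion.

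None of this supplies a per-subject count of rises that does not rest on AE reporting.

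**Conclusion.** The point holds as an inexpensive improvement. Section 19.6.3 does not deliver the whole-study view in Section 19.3.2, and rises outside scheduled visits, or short of the Section 20.5 limits, are counted per subject only if the investigator reports them. The by-visit summary can therefore understate the number of subjects affected.

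That it does understate the harm is a stronger reading, and it is not shown. The documents give no blood pressure SD or event rate, so the size cannot be derived. The 0.6 to 6.1 mm Hg shift and the 4.1 to 6.1 mm Hg half-width rest on the assumed inputs above; they show only that a few sizeable rises can be hard to see in by-visit means. Rises that were treated, or that led to withdrawal, would largely appear in the AE or disposition tables. The separate SAP may already close the gap.

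**What to change.** Add to Section 19.6.3, or to the separate SAP, for the Safety Population by arm:

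1. The number and percentage of subjects, with 90% Wilson CI, having any post-dose systolic reading above 140 or diastolic above 90 mm Hg, among subjects within both limits at baseline. Show it for all readings and for scheduled readings only.
2. The number meeting the Section 20.5 blood pressure definition.
3. Each subject's maximum post-dose change from baseline, summarised from first dose to Day 21 and over the whole study.
4. A statement of the visit to which early-termination readings are assigned.

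The limits serve as reporting cut-offs only and imply no clinical rule. Separately, reconcile the screening wording in Section 17.6 with inclusion criterion 10. Keep the by-visit summaries.

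**Cost.** One or two more tables from data already collected; no added visits or procedures. Single readings near a limit will cross by chance in both arms, and unscheduled readings are taken more often in symptomatic subjects. The between-arm comparison and the scheduled-only version should therefore be read together.

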19.6.4. Other Safety Analysis

Other safety assessments including physical examinations, weight, and pregnancy testing, will be analyzed with appropriate summary statistics.

19.7. Quality of Life/ Health Outcomes Analysis

The change from baseline in [REDACTED] will be summarized with mean change, SD, and 90% CI.

19.8. Interim Analysis

No interim analyses are planned for this study.

19.9. Statistical Power and Sample Size Considerations

It is expected that 66 subjects will be randomized into 1 of 2 treatment groups: 80 U (1 mL) of Acthar per day for 14 consecutive days or placebo (1 mL) per day for 14 consecutive days in a 1:1 ratio (33 per group). The primary analysis is to generate point estimates and associated 90% CIs for the response rates on EDSS in the Acthar group and the placebo group at Day 42, respectively using a mITT analysis population. Assuming 3 subjects will not qualify for the mITT analysis population after randomization in each treatment group, there will be 30 mITT subjects in each group. Based on an expected 60% response rate in the Acthar group, the study can build a 90% Wilson CI of (45.1%, 73.3%) with approximate precision of 14.1%. Based on an expected 25% response rate in the placebo group, the study can build an approximate 90% Wilson CI of (15.7%, 41.5%) with approximate precision of 12.9%.

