Early placebo controlled studies of Acthar for MS relapses demonstrated faster recovery when compared to placebo (Rose et al, 1970). Trials comparing Acthar to corticosteroids in the treatment of MS relapses demonstrated similar marked improvement outcomes (Miller et al, 1961; Thompson et al, 1989). Acthar has been shown to provide positive outcomes and lower numbers of adverse events (AE) compared to intravenous methylprednisolone (IVMP) in MS patients who failed treatment with methylprednisolone (Berkovich et al, 2012).

Although IVMP 1 g per day, high dose oral prednisone (1,250 mg per day), or high dose oral methylprednisolone (1,000 mg per day) for 3 to 5 days has become the standard of care for patients who have experienced MS relapses, many patients do not recover to their baseline level of neurological function. In a retrospective study, (Lublin, 2003) showed that MS relapses result in sustained accumulation of disability over time. In this study, a total of 224 patients who had participated in the placebo groups of large clinical trials and who had experienced MS relapses were evaluated. Forty-two percent of patients were left with a residual deficit of at least 0.5 points on the Expanded Disability Status Scale (EDSS) and 28% with a deficit of at least 1.0 EDSS points at a mean of 64 days following the relapse.

Randomized clinical trials that have examined the response rate of patients who have been treated for MS relapse with either IVMP or oral methylprednisolone suggest that between 65% and 85% experienced significant improvement (Le Page et al, 2015; Sellebjerg et al, 1998). This indicates that 20% to 35% of patients do not experience significant improvement.

There are very limited treatment alternatives for patients who have experienced a relapse of MS and do not respond to corticosteroids. In a randomized, controlled, double blind trial of plasma exchange vs sham treatment in patients with acute demyelinating episodes (including some MS patients) who had failed to respond to treatment with IVMP, 42.1% responded to plasma exchange as compared to only 5.9% who responded to a sham treatment (Weinshenker et al, 1999).

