19.5. Efficacy Analysis

A responder on EDSS is defined as a subject who achieves the following:

- ≥ 1.0 point improvement on EDSS score compared to baseline if baseline EDSS score was ≤ 5.5 .
- ≥ 0.5 point improvement on EDSS score if the baseline EDSS score was > 5.5 .

A responder on MSIS-29 is defined as a patient who achieves ≥ 8 point improvement on the physical subscale score of MSIS-29 compared to baseline.

Baseline is defined as the value observed prior to first dose of the study drug (Day 1).

The primary efficacy endpoint, the response rate on EDSS at Day 42, will be calculated by treatment group. Response rates and 90% Wilson CIs will be reported for each treatment group. These analyses will be performed for the mITT and Per-Protocol populations.

Summary statistics (n, mean, SD, median, minimum, and maximum) of the baseline value, the value at each scheduled postbaseline evaluation and the corresponding change from baseline for EDSS score will be presented by treatment group for all subjects in the mITT population and the Per-Protocol population.

A subject-by-subject data listing sorted by treatment group and subsequently by subject will be generated for all subjects in the mITT population.

For the secondary endpoints, the response rate endpoints will be analyzed and presented with the same approach as described above for the primary efficacy endpoint. The mean score endpoint will be calculated by treatment group. Mean, SD, and 90% CI will be presented by treatment group. All secondary efficacy analyses will use the mITT population.

For the exploratory endpoints, scores change from baseline will be calculated by treatment group. Mean, SD, and 90% CI will be presented by treatment group. All exploratory efficacy analyses will use the mITT population.

For all efficacy endpoints, the normality assumption of the data will be examined using appropriate normality test. If the test result shows the data is not normally distributed, then median, 10% and 90% percentiles will be presented instead of mean, SD and 90% CI.

The statistical analysis plan will describe in further detail the analyses for primary, secondary, and exploratory efficacy endpoints.

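### The placebo 90% Wilson interval in 19.9 and the Synopsis belongs to 8/30 (26.7%), not to the stated 25% rate

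*Combined protocol and SAP*

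**What the plan says.** Section 19.5 fixes the method: "Response rates and 90% Wilson CIs will be reported for each treatment group". Section 19.9 supplies the other inputs. Allocation is "in a 1:1 ratio (33 per group"), three subjects per arm are assumed lost to the mITT population, and so "there will be 30 mITT subjects in each group".

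Two precision statements follow. At an expected 60% response on Acthar, "the study can build a 90% Wilson CI of (45.1%, 73.3%) with approximate precision of 14.1"%. For placebo, "Based on an expected 25% response rate in the placebo group, the study can build an approximate 90% Wilson CI of (15.7%, 41.5"%), with a stated precision of 12.9%. The Synopsis (Sample Size) repeats both.

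The placebo interval is called approximate and the Acthar interval is not. Neither section mentions 8 responders, 26.7%, or any rounding of the count.

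**The concern.** The study is a pilot whose primary analysis is estimation. Section 19.9 contains no hypothesis test and no power calculation, so the two precision statements are the only quantitative support for the sample size. A reader who puts the stated rate and sample size into the stated formula should get the stated interval. That works for Acthar and fails for placebo. At stake is whether the justification can be checked from what is printed; the number of subjects is not in question.

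**Working it through.** **Inputs.** Two-sided 90% Wilson interval (19.5), so z = 1.645 and z² = 2.7055. n = 33 − 3 = 30 per arm (19.9). Expected rates 60% and 25% (19.9).

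**Formula.**

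- Centre = (p + z²/2n) / (1 + z²/n)
- Half-width = z·√[p(1−p)/n + z²/4n²] / (1 + z²/n)

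For n = 30: z²/2n = 0.04509, z²/4n² = 0.000752, and 1 + z²/n = 1.09018.

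**Acthar first, as a check on the method.** With p = 0.60:

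- Centre = 0.64509 / 1.09018 = 0.5917
- Half-width = 1.645 × √(0.008000 + 0.000752) / 1.09018 = 0.1411
- Interval 45.06% to 73.29%, half-width 14.11. This matches the printed 45.1%, 73.3% and 14.1%.

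**Placebo at the stated rate.** With p = 0.25:

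- Centre = 0.29509 / 1.09018 = 0.2707
- Half-width = 1.645 × √(0.006250 + 0.000752) / 1.09018 = 0.1262
- Interval 14.44% to 39.69%, half-width 12.62. This does not match the printed 15.7%, 41.5% and 12.9%.

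**Working back from the printed interval.** Its midpoint is (15.7 + 41.5)/2 = 28.6%. Solving the centre formula for p gives 0.286 × 1.09018 − 0.04509 = 0.267, which is 8/30.

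**Placebo at whole-number counts.**

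| Rate used | Lower | Upper | Half-width |
|---|---|---|---|
| Printed | 15.7 | 41.5 | 12.9 |
| 25% exactly | 14.44 | 39.69 | 12.62 |
| 8/30 = 26.7% | 15.73 | 41.46 | 12.86 |
| 7/30 = 23.3% | 13.18 | 37.90 | 12.36 |

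Only 8/30 matches. In a search over every whole-number count for n from 10 to 69 it was the only pair that gave both printed limits.

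**Size of the discrepancy, 8/30 against 25%.** Lower limit 15.73 − 14.44 = 1.29 points; upper limit 41.46 − 39.69 = 1.77 points; half-width 12.86 − 12.62 = 0.24 points.

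**Other explanations, all at 25%.**

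- *A different n.* The lower limit rises with n and the upper limit falls. A lower limit of 15.7% needs n of about 41 and an upper limit of 41.5% needs n of about 24, so no single n gives both. The 33 randomised per arm give 14.83% to 38.96%.
- *Continuity-corrected Wilson, n = 30.* 13.18% to 41.46%. The upper limit agrees but the lower does not, and the same method gives 43.45% to 74.72% for Acthar, which breaks the line that now reproduces.
- *Another method at 90%, n = 30.* Wald 12.0% to 38.0%; Clopper-Pearson 12.7% to 41.2%; Agresti-Coull 14.3% to 39.8%; Jeffreys 14.0% to 39.4%. None fits.
- *Another confidence level, Wilson, n = 30.* 95% gives 13.0% to 42.7% and 80% gives 16.4% to 36.3%. Neither fits.

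**A separate clerical point in 9.1.** The text says that trials "suggest that between 65% and 85% experienced significant improvement", then "This indicates that 20% to 35% of patients do not experience significant improvement". The complement of 65% to 85% is 15% to 35% (100 − 85 = 15; 100 − 65 = 35). The documents do not show which figure slipped, and nothing is calculated from it.

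**The case against.** The sponsor could fairly reply that this is rounding and not a miscalculation. A quarter of 30 is 7.5 subjects, which cannot be observed; the study will report intervals on whole counts, and 8 is one of the two nearest. The formula was applied correctly to that count. The qualifier *approximate* appears on the placebo interval and not on the Acthar one, where 18/30 is exactly 60%, which suggests the authors knew. The plan sets no precision target that 12.9 would meet and 12.6 would miss, and a later sample-size calculation would presumably use the observed rates and not this planning interval.

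Most of this stands, and it limits the point to one of disclosure. It does not remove it. *Approximate* does not tell the reader that the rate moved from 25% to 26.7%, nor that 7.5 was rounded up and not down. Rounding down would have given limits 2.55 and 3.56 points below the 8/30 limits (15.73 − 13.18 and 41.46 − 37.90). The limits are also printed to a tenth of a point while being more than a full point from those for 25%.

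**Conclusion.** The concern holds. The placebo interval and precision in 19.9 and the Synopsis are wrong for the rate printed beside them and right for 8/30. That the figures belong to 26.7% is established by calculation; that 7.5 was rounded up is an inference, though no other explanation tried fits. The result rests only on the plan's own inputs: Wilson method, 90% level, n = 30.

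The consequence is minor. The plan states slightly less precision than a 25% rate would give, and neither the sample size nor any analysis changes. It should still be corrected, because it is half of the only numerical argument for the sample size. The mismatch in 9.1 is background text and carries no weight in this conclusion.

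**What to change.** In 19.9 and in the Synopsis, do one of the following:

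- give (14.4%, 39.7%) with precision 12.6% for a 25% placebo rate; or
- keep (15.7%, 41.5%) with precision 12.9% and state that these are for 8 of 30 responders (26.7%), the nearest whole count above 25%.

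The second has the advantage of describing an interval the study could actually observe. In 9.1, check the two sentences against the cited trials and make them agree.

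The cost is one pair of limits with its precision, or one short clause, in two places, plus a check of two background sentences. Nothing changes in the number randomised, the analysis or the conduct of the study.
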